5.3.1.2. Multiple Imputation for Exploratory Analyses

A second multiple imputation will be performed similarly for each assessment, utilizing the data through Month 6, for exploratory efficacy analyses performed after the completion of the safety follow-up period. For each of the initial 20 imputations created through Month 3, an additional 20 imputations will be created to impute Month 4.5 and Month 6. Subsequent analyses of the 20×20=400 imputations will be performed separately for each imputation, then results combined using PROC MIANALYZE.

The following pseudocode will be used, in addition to the prior pseudocode:

```

proc mi data=yyy (rename=( _imputation_ =Imp1)) seed=1357902 nimpute=20 out=zzz
  minimum = 0 0 0 18 0 0 0  0  0  0  0  0  0
  maximum = 1 1 1 99 1 1 1  xx xx xx xx xx xx
  round =   1 1 1 1  1 1 1  1  1  1  1  1  1 ;

  by Imp1;

var Dur5yr MGSless6 male age trt0_5 trt1_0 trtpbo
    Day1 Day14 Day45 Day90 Day135 Day180;

mcmc chain=multiple displayinit;
run;

```

5.3.2. Last Observation Carried Forward

The LOCF approach will be used to impute primary efficacy data for sensitivity analyses, where specified. Post-baseline values may be carried forward (i.e., scheduled visits at Day 14 or later, any post-baseline unscheduled or early termination visits that occur on or after Day 14), but values prior to first application of randomized study treatment will not be used for imputation. Further details are provided in [Section 8.1.2](#).

6. DEMOGRAPHICS AND BASELINE CHARACTERISTICS

6.1. Patient Disposition and Withdrawals

Patient disposition and follow-up will be summarized by treatment group and overall, reflecting completion or withdrawal through Month 3. This disposition summary will be based on the ITT Set, and will tabulate inclusion in analysis sets, completion status, and reason for withdrawal. Numbers of screen failures will also be presented.

Reason for screen failures and reason for withdrawal before treatment assignment/randomization will be listed separately from completion and withdrawal information for patients enrolled in the study.

After the completion of the safety follow-up period, an additional summary of disposition through Month 6 will be created as part of the supplemental safety analyses.

6.2. Demographic and Other Baseline Characteristics

Demographic data and baseline disease characteristics will be summarized by treatment, using the Safety and ITT analysis sets. Demographic data will include age, sex, childbearing potential (if applicable), race, and ethnicity. Baseline characteristics will include height, weight, duration of meibomian gland disease (i.e., <5 years or ≥ 5 years), study eye (left or right), and baseline MGS score in the study eye (<6 or $6-12$).

6.3. Medical History

Non-ophthalmic history will be recorded by body system, medical condition, or surgery, and start and end dates. Ophthalmic history will be recorded by specific location (e.g., left lower eyelid or right eye); ocular disease, condition, or procedure; start and end dates; and whether medication is currently being taken for that condition. All medical history will be coded according to the Medical Dictionary for Regulatory Activities (MedDRA[®]), using System Organ Class (SOC) and Preferred Term (PT).

Ophthalmic and non-ophthalmic medical history will be summarized separately by treatment, SOC, and PT, using the Safety Set. The number and percent of patients with ophthalmic and non-ophthalmic history will also be presented.

Non-Ophthalmic and ophthalmic medical history will be listed separately.

7. PROTOCOL DEVIATIONS

All protocol deviations will be identified, categorized, and graded by the investigator and an interdisciplinary team. An additional review by a multi-disciplinary team, for adherence to the grading, will be completed prior to database freeze, and unmasking of specific study personnel. Please refer to [Protocol Deviation Definitions – Three Month Analysis](#) for additional details regarding protocol deviation definitions and classifications.

Deviations will be graded as one of the following:

- Grade 1: No impact on data quality or patient safety
- Grade 2: Minor impact on data quality
- Grade 3: Minor impact on patient safety
- Grade 4: Major impact on data quality or patient safety
- Grade 5: Death

All patients with Grade 4 or Grade 5 deviations affecting Baseline through Month 3 will be excluded from the PP analysis set. All patients with Grade 4 or Grade 5 deviations affecting Baseline through Month 6 will be excluded from the PP6 analysis set.

Grade 2, 3, 4, and 5 protocol deviations through Month 3 will be summarized by deviation type, grade, and treatment, as well as listed by patient. As part of the supplemental safety analyses, Grade 2, 3, 4, and 5 protocol deviations through Month 6 will be similarly summarized and listed.

8. EFFICACY

Efficacy analyses will be performed on the ITT Set. The primary analyses will be repeated on the mITT Set (if different from the ITT Set) and PP Set. If the primary analyses are notably different between the ITT and mITT sets, additional analyses of the other efficacy endpoints may be performed on the mITT Set.

In addition to those analyses, which are performed at the 3-month time point, additional exploratory analyses will be performed at the 6 month time point, using data collected during the 3 month safety follow-up period. These analyses will also be performed on the ITT Set, with MGYLS and OSDI total score analyses repeated on the mITT and PP6 sets. P-values for analyses of data collected during the 3-month safety follow-up period (e.g., Month 4.5 and Month 6) are provided for descriptive purposes only.

Endpoints will be summarized descriptively, for all scheduled assessment time points. Actual values and changes from baseline will be summarized descriptively for all time points at which the endpoint is collected.

Dichotomous endpoints will be analyzed using a CMH test to compare each AZR-MD-001 treatment arm to placebo, controlling for disease duration category and baseline MGS score category. If CMH comparisons are not estimable, Pearson's chi-square or Fisher's Exact will be used, as described in [Section 8.2](#) and [Section 8.3](#).

8.1. Primary Efficacy Endpoints and Analysis

These endpoints will be analyzed using the ITT, mITT, and PP sets, with the primary analysis being performed on the ITT Set. Multiple imputation will be applied, unless otherwise indicated. Responder criteria based on eye-specific measurements (MGYLS, etc.) are calculated for the study eye only. These analyses will include all data collected through Month 3.

8.1.1. Primary Efficacy Endpoints

The primary efficacy variables are:

- change from baseline to Month 3 in MGYLS
- change from baseline to Month 3 in OSDI total score

The primary efficacy endpoints will be evaluated using the following hierarchical approach. For each endpoint, the subsequent endpoint will not be evaluated unless the prior endpoint is significant at $\alpha=0.05$. Therefore, this hierarchical approach controls for the family-wise Type I error and does not require adjustment for multiplicity, as per [Dmitrienko and D'Agostino, 2013](#).

- a) Change from baseline to Month 3 in MGYLS, comparing AZR-MD-001 0.5% to placebo.
- b) Change from baseline to Month 3 in OSDI total score, comparing AZR-MD-001 0.5% to placebo.
- c) Change from baseline to Month 3 in MGYLS, comparing AZR-MD-001 1.0% to placebo.
- d) Change from baseline to Month 3 in OSDI total score, comparing AZR-MD-001 1.0% to placebo.

Multiple imputation will be applied, as described in [Section 5.3](#). Analyses will be performed as follows.

Change from baseline in MGYLS will be analyzed at Month 3 using an ANCOVA model with (continuous) baseline MGYLS score as a covariate and treatment (AZR-MD-001 ointment/semi-

solid drug or placebo), duration of disease category (i.e., <5 or ≥ 5 years), and baseline MGS score category (< 6 or ≥ 6 and ≤ 12) as factors in the model. This ANCOVA model will also be performed for each AZR-MD-001 ointment/semi-solid drug dosing level versus placebo. The least square means for the differences between treatments will be presented along with two-sided (95%) confidence intervals.

The following pseudocode will be used:

```
PROC GENMOD data=xxx;  
  BY visit;  
  CLASS treatment (ref = 'AZR-MD-001 PLACEBO') duration baseMGS;  
  MODEL chg =treatment base duration baseMGS;  
  LSMEANS treatment;  
run;
```

Change from baseline in OSDI total score will be analyzed at Month 3 using the same methodology as the change from baseline in MGYLS, using an ANCOVA model with (continuous) baseline OSDI total score as a covariate and treatment, duration of disease category, and baseline MGS score category as factors in the model.

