5.1 INCLUSION CRITERIA

- Male or female, 18 years of age or older at screening visit
- Capable of understanding and willing to provide written informed consent and likely to complete the entire course of study according to instructions
- Written authorization for use and release of health and research study information has been obtained
- Best-corrected visual acuity (BCVA) of 20/40 or better (Snellen equivalent), using the logarithm of the minimum angle of resolution (LogMAR) in each eye at the screening and baseline visits
- Evidence of meibomian gland obstruction (based on a meibomian gland secretion (MGS) score of ≤ 12 for 15 glands of the lower lid) in both eyes at the screening and baseline visits
- Reported dry eye signs and symptoms within the past 3 months
- Prior to starting screening visit procedures, patients are required to have discontinued:
 - Use of systemic antihistamines or isotretinoin for at least 1 month
 - Anti-inflammatory treatments for DED (e.g., cyclosporine ophthalmic emulsion [Restasis® or Ikervis®] or lifitegrast ophthalmic solution [Xiidra®]) for at least 3 months
 - All other prescription medications used for dry eye or MGD (e.g., antibiotics, corticosteroids, and non-steroidal anti-inflammatory drugs) for at least 2 weeks
 - LipiFlow® or other lid-heating therapy, meibomian gland probing, or therapeutic gland expression in either eye within 6 months prior to the screening visit
 - All other MGD treatments (e.g., at-home warm compress therapy, eyelid hygiene, eyelid massage, and manual lid expression) for at least 2 weeks
- And
 - All other topical ophthalmic preparations (including artificial tear substitutes) other than the study drops: 72 hours prior to screening visit. If artificial tear substitutes were used within 72 hours of the screening visit the visit should be rescheduled
- Evidence of MGD at the screening and baseline visits:
 - Score ≥ 6 on the Standard Patient Evaluation of Eye Dryness questionnaire (SPEED)
 - Ocular Surface Disease Index (OSDI) questionnaire score ≥ 13 and < 34
- And
 - TBUT < 10 seconds in both eyes

- Demonstrated ability to follow dosing instructions at the baseline visit
- A negative pregnancy test result for all women of childbearing potential at the screening visit

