6.1.3 DOSING AND ADMINISTRATION

For Cohort 1, the study medication will be self-administered by the patient (or administered by a caregiver) at the study site after all procedures have been completed for the run-in and post-randomization visits. At these visits, each patient will be asked to stay at the site for 30 minutes after study drug administration. No other dosing will be done in office as the product will be dosed in the evening only.

For the Expansion Cohort, the study medication will be self-administered by the patient at the study site after all procedures have been completed for the baseline visit only using "Vaseline". At this visit, each patient will be asked to stay at the site for 30 minutes after study drug administration. No other dosing will be done in office as the product will be dosed in the evening only.

Patients (or a caregiver) will apply a dose of approximately 5 mg using a dosing aid supplied by Azura Ophthalmics. Patients will then use their washed index finger (Cohort 1 and Expansion Cohort) or an applicator (Cohort 1 only) to apply the drug to the tarsus of the lower lid of both

eyes in the evening just before bedtime. The patient will then blink several times to transfer a portion of the drug from the lower eyelid to the upper eyelid (see the Dosing Instruction Sheet for more detail).

During the double-masked treatment period, each patient (or caregiver) must apply 1 application of the assigned treatment in the evening to the tarsus of the lower lid of both eyes.

Multi-dose tubes of the masked study medication are each to be used for only 30 days to both eyes. The patient should be instructed to place the used tube in the used tube bag after 30 days and should return used and unused tubes at the next study visit to the study site.

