2.2. Brief Description

The study is a multi-center, double-masked, placebo-controlled, randomized, parallel group study carried out in 2 sequential cohorts. The Expansion Cohort includes parallel doses of 2 concentrations of AZR-MD-001 ointment/semi-solid drug (0.5% and 1.0%) and placebo, dosed twice-weekly in the evening. Patients are to be followed for 6 months. Primary efficacy analyses will be performed based on the 3-month data, and exploratory efficacy analyses will be performed on data collected during the subsequent 3-month safety follow-up.

Inclusion and exclusion criteria are provided in [AZ201801 Protocol Sections 5.1](#) and [Section 5.2](#).

Key inclusion criteria require patients have meibomian gland secretion (MGS) scores of ≤ 12 in both eyes at the Screening and Baseline visits; reported dry eye signs and symptoms within the past 3 months; Standard Patient Evaluation of Eye Dryness questionnaire (SPEED) score ≥ 6 ; OSDI questionnaire total score ≥ 13 and < 34 ; and tear break-up time (TBUT) < 10 seconds in both eyes.

Exclusion criteria include best corrected visual acuity (BCVA) worse than 20/40 in either eye; anticipated contact lens use; Schirmer's tear test without anesthesia ≤ 5 mm in either eye at the baseline visit; or corneal staining ≥ 3 (between 33 and 100 dots) using the Oxford Scheme.

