5.2.2. Baseline Values

The baseline assessment will be the last available measurement taken on or before the date of first dose of study treatment, including any assessments at unscheduled visits. Measurements taken on the date of first dose of study treatment will be considered to be taken prior to first dose. Baseline values are typically collected at the Baseline visit.

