5.3.1.1. Multiple Imputation for Primary Analysis

Multiple imputation will be performed separately for each assessment; in other words, MGYLS values will not be used to impute OSDI values. The same seed number (utilized in SAS[®] PROC MI) of 135790 will be used throughout. For each MI, 20 imputations will be created, analyses performed on each imputed dataset separately, and results combined using PROC MIANALYZE. The appropriate minimum and maximum values will be used for each variable, and results rounded to the same precision as collected values. Multiple imputation will be limited to patients in the analysis population being used, and will include values that are eligible for use in summaries and analyses as described in [Section 5.1](#) (e.g., unscheduled and early termination visits will be mapped to scheduled visits, and visits with >1 non-missing values mapped to that visit will utilize the later result), through the Month 3 visit. Screening visit values will not be incorporated into the multiple imputation.

The following variables will be included in the multiple imputation model, as numeric variables:

- Treatment group (split into three dichotomous variables)
- Randomization criteria (disease duration category and baseline MGS score category)
- Age
- Sex
- Analysis value (MGYLS or OSDI total score) for each scheduled visit

The following pseudocode will be used:

```
proc mi data=xxx seed=135790 nimpute=20 out=yyy  
    minimum = 0 0 0 18 0 0 0 0 0 0 0
```

```

        maximum = 1 1 1 99 1 1 1  xx xx xx xx
        round =   1 1 1 1  1 1 1  1  1  1  1  ;
var Dur5yr MGSless6 male age trt0_5 trt1_0 trtpbo
    Day1 Day14 Day45 Day90;
mcmc chain=multiple displayinit;
run;

```

<proc genmod, etc.>

```

Proc mianalyze data=xxx (drop=effect);
  by trt01pn;
  modeleffects LSM;
  stderr;
run;

```

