Table 35A Shift Table of Ophthalmoscopy Lens Status Through Month 3 – Expansion Cohort (Safety Set)

Table 35B Shift Table of Ophthalmoscopy Details Through Month 3 – Expansion Cohort (Safety Set)

Table 36 Shift Table of Intraocular Pressure Through Month 3 – Expansion Cohort (Safety Set)

Table 37 Shift Table of Meibography/Meiboscopy Results Through Month 3 – Expansion Cohort (Safety Set)

Listing 1 Patient Disposition and Analysis Set Inclusion Through Month 3 – Expansion Cohort

Listing 2 Inclusion and Exclusion Criteria Not Met and Screen Failure Information – Expansion Cohort

Listing 3 Patient Demographics and Baseline Characteristics – Expansion Cohort

Listing 4 Ophthalmic Medical History – Expansion Cohort

Listing 5 Non-Ophthalmic Medical History – Expansion Cohort

Listing 6 Grade 2 or Higher Protocol Deviations Through Month 3 – Expansion Cohort

Listing 7 Patient Visits Through Month 3 – Expansion Cohort

Listing 8 Meibomian Gland Evaluation (MGS, MGYLS, MGYOLS) Through Month 3 – Expansion Cohort

Listing 9 Ocular Surface Disease Index (OSDI) Through Month 3 – Expansion Cohort

Listing 10 Standard Patient Evaluation of Eye Dryness (SPEED) Through Month 3 – Expansion Cohort

Listing 11 Visual Analogue Scale (VAS) Responses Through Month 3 – Expansion Cohort

Listing 12 Tear Break-up Time (TBUT) Through Month 3 – Expansion Cohort

Listing 13 Schirmer's Assessment Results, without Anesthesia, Through Month 3 – Expansion Cohort

Listing 14 Slit Lamp Examination, Including Erythema, Telangiectasias, and Conjunctival Hyperemia Through Month 3 – Expansion Cohort

Listing 15 Lissamine Green and Sodium Fluorescein Staining, Oxford Scale Through Month 3 – Expansion Cohort

Listing 16 Study Drug Dispensation, Return and Compliance Through Month 3 – Expansion Cohort

Listing 17 Physician Observation of Vaseline Application at Baseline Visit

Listing 18A Adverse Events Through Month 3 – Expansion Cohort

Listing 18B Serious Adverse Events Through Month 3 – Expansion Cohort

Listing 18C Adverse Events Leading to Drug Withdrawal Through Month 3 – Expansion Cohort

Listing 18D Adverse Events Due to Vaseline Application at Baseline Visit– Expansion Cohort

Listing 19 Prior and Concomitant Ophthalmic Medications Through Month 3 – Expansion Cohort

Listing 20 Prior and Concomitant Non-Ophthalmic Medications Through Month 3 – Expansion Cohort

Listing 21 Urine Pregnancy Test Results Through Month 3 – Expansion Cohort

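### A free but modest precision gain is left unused: the primary ANCOVA and the imputation ignore the Screening readings of MGYLS and OSDI

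*SAP*

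**What the plan says.** Both schedules of activities (Protocol Table 1, SAP Table 2) place OSDI and the meibomian gland evaluation at Screening and again at Baseline. MGYLS comes from that evaluation; SAP Appendix 4 lists it under "Meibomian Gland Evaluation (MGS, MGYLS, MGYOLS) Through Month 3". The entry criteria also rely on both visits: SAP 2.2 requires MGS "scores of ≤ 12 in both eyes at the Screening and Baseline visits", and Protocol 5.1 places the SPEED, OSDI and TBUT limits under "Evidence of MGD at the screening and baseline visits".

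The Expansion Cohort has no run-in treatment. Its Vaseline practice dose is "self-administered by the patient at the study site after all procedures have been completed for the baseline visit only" (Protocol 6.1.3), so both readings precede any ointment.

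For analysis, SAP 5.2.2 defines a single value: "The baseline assessment will be the last available measurement taken on or before the date of first dose of study treatment". SAP 8.1.1 then specifies: "Change from baseline in MGYLS will be analyzed at Month 3 using an ANCOVA model with (continuous) baseline MGYLS score as a covariate", plus treatment, disease-duration category and baseline MGS category. OSDI is handled the same way with its own baseline. SAP 5.3.1.1 imputes from the Baseline, Day 14, Month 1.5 and Month 3 values and adds: "Screening visit values will not be incorporated into the multiple imputation". Neither that section nor the list of changes in SAP 12 gives a reason.

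**The concern.** An examiner's gland score and a one-week-recall questionnaire are both noisy. Two pre-treatment readings usually describe a patient's underlying level better than one, so adjusting for both can reduce the residual variance of both primary endpoints. Both readings precede randomization, so a covariate fixed before unmasking cannot bias the comparison or inflate type I error. Because Baseline stays in the model and remains the reference for change, the treatment difference being estimated is the same.

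What is at stake is precision only. The four primary tests run in strict sequence (SAP 8.1.1), so a gain at any step also helps the later ones reach testing.

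**Working it through.** **Inputs.** SAP Table 1 SDs of change (0.5% / 1.0% / placebo): MGYLS 3.35 / 4.11 / 2.28; OSDI 9.06 / 8.39 / 6.31. Differences from placebo: MGYLS 0.5%, 2.77 − 0.77 = 2.00; OSDI 1.0%, −5.33 − (−0.81) = −4.52. There are 75 patients per arm and alpha is two-sided 0.05. The correlations are assumptions.

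**The plan's own figures.** A two-sample t-test with noncentral t reproduces:
- 72 per arm for 95% power, from OSDI 1.0% (SDs 8.39 and 6.31);
- 0.918 for MGYLS 0.5% with pooled SD 3.63 and 75 per arm (SAP 2.3.2).

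**Variance ratio.** Let a = corr(Baseline, Month 3), b = corr(Screening, Month 3) and r = corr(Screening, Baseline). Residual variance with both readings, relative to Baseline alone, is

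R = 1 − (b − a·r)² / [(1 − r²)(1 − a²)].

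If all three equal rho, this becomes (1 + 2rho)/(1 + rho)².

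| a | b | r | R | Reduction |
|---|---|---|---|---|
| 0.7 | 0.7 | 0.7 | 0.830 | 17% |
| 0.5 | 0.5 | 0.5 | 0.889 | 11% |
| 0.3 | 0.3 | 0.3 | 0.947 | 5% |
| 0.5 | 0.5 | 0.7 | 0.941 | 6% |
| 0.3 | 0.3 | 0.5 | 0.967 | 3% |
| 0.2 | 0.2 | 0.8 | 0.995 | 0.5% |
| 0.5 | 0.45 | 0.7 | 0.974 | 3% |
| 0.5 | 0.4 | 0.7 | 0.993 | 0.7% |
| 0.5 | 0.35 | 0.7 | 1.00 | 0% |

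The first three rows are favourable: they assume that readings at most about two weeks apart agree no better than readings three months apart. The last three let correlation fall with time.

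**Entry range.** A simulation kept only patients with OSDI from 13 to below 34 at both visits. With equal correlations of 0.5 to 0.8 before selection, R was 0.894 to 0.986, a gain of 1% to 11%.

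**Dilution.** Suppose Screening removes the same absolute variance in each arm and the extra active-arm variance is unrelated to the pre-dose readings. For OSDI 1.0% versus placebo, the mean variance is (8.39² + 6.31²)/2 = (70.39 + 39.82)/2 = 55.10. A proportional gain in the placebo arm shrinks by 39.82/55.10 = 0.72, so 11% becomes about 8%. For MGYLS 0.5% the factor is 2.28²/[(3.35² + 2.28²)/2] = 5.20/8.21 = 0.63.

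**Power at 75 per arm, Table 1 SDs** (each multiplied by √R):

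| Comparison | R = 1 | 0.97 | 0.95 | 0.92 |
|---|---|---|---|---|
| MGYLS 0.5% (SD 2.865) | 0.989 | 0.991 | 0.992 | 0.993 |
| OSDI 1.0% (SD 7.423) | 0.960 | 0.964 | 0.967 | 0.971 |

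MGYLS 1.0% and OSDI 0.5% already exceed 0.999. Using SDs of change as the one-covariate residual SD is conservative for the absolute power.

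**The case against.** The planned ANCOVA is standard, prespecified and unbiased, and on Table 1 assumptions the trial is already well powered. The comparison that gains most, OSDI 1.0%, is last in the hierarchy. All of that stands.

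The two readings may also not be clean replicates. Screening procedures can be spread over Days −14 to −2, so the gap may be as short as two days. OSDI asks about the past week, while artificial tears need stop only 72 hours before Screening, so the two recall windows may overlap or reflect different conditions. The baseline MGS category and the MGS limit at both visits restrict what Screening MGYLS can add, and the simulation covers OSDI only. These points shrink the gain, possibly to nothing, but do not make the extra covariate harmful.

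Several stronger readings are tempting but unsupported:
- **Screening as the best predictor in the model.** Baseline is in the model. Under equal correlations Screening only matches it, and otherwise would usually predict less well. It can add to Baseline and to the categorical factors; it does not outrank Baseline.
- **The Screening data are discarded.** They decide eligibility, and under SAP 5.2.2 they become the baseline if the Baseline-visit value is missing.
- **Power rising from 0.918 to as much as 0.957.** The 0.918 for MGYLS 0.5% is a pooled-SD figure that SAP 2.3.2 derives only as a reference for the re-estimation. The upper end needs R = 0.83 with no dilution.
- **A clear improvement in imputation.** No dropout rate is given, and Day 14 and Month 1.5 values are already included, so the benefit is probably small.
- **Fewer patients added at re-estimation.** That rule uses the masked pooled SD of raw changes, which a covariate does not alter.

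**Conclusion.** The point holds as a free improvement, not as a defect. Two pre-dose readings of each primary measure exist, the primary model adjusts for one, and the imputation explicitly excludes the other. Using both should cut residual variance by roughly 0% to 11% in plausible cases, with 17% as an upper bound that requires equal correlations of 0.7, and by less in the pairwise comparisons after dilution. In power terms this is about 0.960 to 0.967 for OSDI 1.0% at a 5% reduction, and essentially no change for MGYLS 0.5%. These sizes rest on assumed correlations and on the Table 1 planning SDs. No conclusion of the trial becomes invalid if the plan stays as it is.

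**What to change.** Before unmasking:

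1. **SAP 8.1.1.** Add the Screening value of the same measure (MGYLS in the study eye; OSDI total score) as a second continuous covariate. Keep Baseline in the model and as the reference for change.
2. **SAP 5.3.1.1.** Replace the exclusion sentence and add the Screening value to the PROC MI VAR list, with matching minimum, maximum and rounding entries. The imputation model should contain every covariate in the analysis model, even if the imputation gain itself is small.
3. **Rules for special cases.** State how the second covariate is set when the Screening value already serves as baseline under SAP 5.2.2. For rescreened patients, use the value from the qualifying screening. Confirm that the SAP 5.1 mapping governs unscheduled pre-Baseline assessments. Say how a missing Screening value is handled in the LOCF analysis.
4. **Consistency.** Carry the change into the SAP 8.1.2 sensitivity models and the Month 6 imputation (SAP 5.3.1.2). Extending it to SPEED, VAS and MGS is optional.

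The cost is one model degree of freedom and edits to a few SAP sentences and pseudocode blocks, with no new data, visit or procedure.
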